1.0 INTRODUCTION

The purpose of this statistical analysis plan (SAP) is to outline the primary statistical analyses for the Cognitive Behavioural Therapy to Optimize Post-Operative Recovery (COPE) trial. We will adhere to the CONSORT 2010 guideline when reporting the results of COPE. The structure of this statistical analysis plan follows the Guidelines for the Content of Statistical Analysis Plans in Clinical Trials.¹ Additional SAPs will be developed for secondary analyses of trial data.

The primary objective of the COPE trial is to determine if cognitive behavioural therapy (CBT), versus usual care, reduces the prevalence of moderate to severe Persistent Post-Surgical Pain (PPSP) over 12 months post-fracture in participants with an open or closed fracture of the appendicular skeleton.

The secondary objectives of the COPE trial are to determine if CBT, versus usual care: 1) increases physical functioning over 12 months post-fracture, 2) improves mental functioning over 12 months post-fracture, 3) accelerates return to function over 12 months post-fracture, 4) reduces pain severity over 12 months post-fracture, 5) reduces pain interference over 12 months post-fracture, and 6) reduces the proportion of participants using opioid class medications at 6 and 12 months post-fracture in patients with an open or closed fracture of the appendicular skeleton.

Details on the trial design, randomization, and sample size have been published previously.²

2.0 TRIAL POPULATION

2.1 Patient Flow through the Trial

The number of patients screened, included, and excluded will be presented in a flow diagram (**Figure 1**). The figure will include the number of participants who were randomly assigned to the two treatment groups. It will also include the number of participants who were subsequently deemed ineligible by the Central Adjudication Committee.

We will summarize the number of patients excluded by reason (**Table 1**) and the number of participants deemed ineligible by the Central Adjudication Committee by reason (**Table 2**). Participants deemed ineligible by the Central Adjudication Committee will not be included in any analysis, as per guidance from Fergusson et al.³

Figure 1 will include participant follow-up and the number of participants who were lost to follow-up, along with the reason, over the course of the trial.

2.2 Participant Demographics, Injury, and Fracture Characteristics, and Surgical and Perioperative Care Details

We will use descriptive measures to summarize participant demographics, baseline information, injury, fracture characteristics, surgical, and perioperative care details of the sample stratified by treatment group (**Tables 3 and 4**). We will use means and standard deviations (SDs) or medians and interquartile ranges (IQR) for continuous data, and categorical data will be presented as frequencies and percentages. We will examine key baseline differences between those who stopped the CBT program early and those who did not. We will not statistically test for differences

in these characteristics between treatment groups (**Section 3.2**). The potential clinical importance of any imbalance between treatment groups will be noted.

Additional details on the trial population have been published previously.²

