3.0 ANALYSIS

3.1 Analysis Methods

The primary and secondary analyses will be conducted following intention-to-treat (ITT) principles, ensuring that participants are analyzed in their originally assigned treatment groups, regardless of adherence or protocol deviations. The date on which the participant's fracture(s) occurred will be used as the starting point for all time-to-event analyses.

We will use multiple imputations to account for missing data in the analyses and minimize potential bias under the assumption that the data are missing at random (MAR). This approach will allow for the uncertainty associated with missing values to be properly accounted for, improving the robustness of statistical inferences.⁴ Additionally, as we anticipate high rates of early withdrawal, we will account for this in the analyses, if needed.

If any of the analysis models fail to converge, we will remove adjustment covariates one by one until convergence is achieved. The same set of covariates will be used consistently across all models in the primary and secondary analyses.

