4.0 FIGURES AND TABLES

Figure 1: Consort Flow Chart for Trial Participants

*Please refer to Table 1 for reasons for exclusion

**Please refer to Table 2 for reasons for ineligibility per the Central Adjudication Committee

***Participants were assessed at follow-up regardless of number of sessions completed

Table 1: Reasons for Exclusion*

Reasons for Exclusion	Total n (%) (n= XX patients excluded)
Patient does not have an eligible fracture	
Patient has a concomitant injury which, in the opinion of the attending surgeon, is likely to impair function for as long as or longer than the patient's extremity fracture(s)	
Patient is facing current or impending incarceration	
Currently not experiencing any pain in the fracture region despite being fully weight bearing	
Patient has active psychosis	
Patient has active suicidality	
Patient has an active substance use disorder that, in the judgement of the treating surgeon, would interfere in the patient's ability to partake in the CBT and/or the study	
Patient does not have the cognitive ability and language skills to participate in CBT	
Patient is already participating in or planning to start other psychological treatments (including CBT) within the duration of the study (12 months)	
Patient does not have consistent online access from a smartphone/internet-enabled device with a minimum operating system able to use the CBT provider's application	
Anticipated problems, in the judgement of study personnel, with the patient participating in CBT intervention and/or returning for follow-up	
Patient is not willing to participate in CBT	
Currently enrolled in a study that does not permit co-enrolment in other trials	
Previously enrolled in the COPE trial	
Patient was not screened/approached within 2-12 weeks following their fracture	
Patient's fracture was not treated operatively with internal fixation	
Patient did not provide informed consent	

*This table shows all response options for the data collected. In the primary manuscript, some data categories may be removed if there are no responses selected.

Table 2: Reasons for Exclusion after Blinded Central Adjudication Committee Review*

Reasons for Exclusion	Number of Patients Excluded Following Adjudication	
	CBT n (%) (n= XX adjudicated as ineligible)	Usual Care n (%) (n= XX adjudicated as ineligible)
Fragility fracture (a fall from a standing height or less, that results in a fracture) as their only extremity fracture treated with internal fixation		

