Stress fracture as their only extremity fracture treated with internal fixation		
Patient has a concomitant injury which, in the opinion of the attending surgeon, is likely to impair function for as long as or longer than the patient's extremity fracture(s)		
Patient is facing current or impending incarceration		
Currently not experiencing any pain in the fracture region despite being fully weight bearing		
Patient has active psychosis		
Patient has active suicidality		
Patient has an active substance use disorder that, in the judgement of the treating surgeon, would interfere in the patient's ability to partake in the CBT and/or the study		
Patient does not have the cognitive ability and language skills to participate in CBT		
Patient is already participating in or planning to start other psychological treatments (including CBT) within the duration of the study (12 months)		
Patient does not have consistent online access from a smartphone/internet-enabled device with a minimum operating system able to use the CBT provider's application		
Anticipated problems, in the judgement of study personnel, with the patient participating in CBT intervention and/or returning for follow-up		
Patient is not willing to participate in CBT		
Currently enrolled in a study that does not permit co-enrolment in other trials		
Previously enrolled in the COPE trial		
Patient was not screened/approached within 2-12 weeks following their fracture		
Patient's fracture was not treated operatively with internal fixation		
Patient did not provide informed consent		
Patient is under 18 years of age		
Another reason to exclude the patient (must be approved by the Methods Centre)		

*This table shows all response options for the data collected. In the primary manuscript, some data categories may be removed if there are no responses selected.

Table 3: Baseline characteristics*

	CBT n (%) (n= XX)	Usual Care n (%) (n= XX)
Age in years, mean (SD)		
Sex		
Female		
Male		
Did not want to disclose		
Body mass index in kg/m ²		
Underweight (BMI < 18.5)		
Normal weight (18.5 – 24.9)		
Overweight (25 – 29.9)		
Obese (BMI ≥ 30)		
Did not want to disclose		
Race or ethnicity		
White		
South Asian		
East Asian		
Southeast Asian		
Middle Eastern		
People of African and/or Caribbean Descent		
Indigenous		
Latinx		
Multiethnic Background		
Did not want to disclose		
Latin or Hispanic origin		
Employment prior to injury		
First responder		
Police officer		
Firefighter		
Emergency medical technician		

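### SAP section 2.1 drops adjudicated-ineligible participants from every analysis without limiting adjudication to pre-randomisation information, so bias in the primary comparison is left possible

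*SAP*

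**What the plan says.** Section 2.1 places the adjudication after random assignment. Of the flow diagram it says: "It will also include the number of participants who were subsequently deemed ineligible by the Central Adjudication Committee". It then sets the rule: "Participants deemed ineligible by the Central Adjudication Committee will not be included in any analysis". A published paper on post-randomisation exclusions is cited in support.

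The grounds are in section 4.0, headed "Table 2: Reasons for Exclusion after Blinded Central Adjudication Committee Review", with counts by arm. Three of them matter here:
- "Patient is not willing to participate in CBT"
- "Anticipated problems, in the judgement of study personnel, with the patient participating in CBT intervention and/or returning for follow-up"
- "Another reason to exclude the patient (must be approved by the Methods Centre", closing bracket omitted

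Section 3.1 commits the primary and secondary analyses to intention-to-treat, "ensuring that participants are analyzed in their originally assigned treatment groups, regardless of adherence or protocol deviations". It also says: "as we anticipate high rates of early withdrawal, we will account for this in the analyses, if needed".

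Section 3.3 lists the sensitivity and exploratory analyses, with shells in Tables 11 and 12. None is run in all randomised participants.

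**The concern.** Removing people who were ineligible at entry need not bias a comparison, provided that the judgement uses only information fixed before randomisation and is made without knowledge of arm or outcome. Section 2.1 states neither condition. Table 2 calls the review blinded but does not say to what.

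The gap matters most for the CBT-related grounds. A participant allocated to CBT is asked to start and may decline. A participant in usual care is not asked. Information bearing on willingness, or on problems with taking part, can therefore accumulate mainly in one arm. A report that someone declined CBT may also reveal the arm to a committee meant to be blind. The remaining ground of the three, the catch-all row, is tied to no stated criterion.

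At stake is the primary analysis set. If early withdrawal is as common as section 3.1 expects, the line between withdrawing from treatment, which stays in the analysis, and being unwilling, which could be coded as ineligible, needs to be written down before results are seen.

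**Working it through.** **1. The passages side by side.** Section 3.1 keeps non-adherent participants in their assigned group. Section 2.1 removes adjudicated-ineligible ones from everything. The two agree if adjudication concerns status at entry only. They conflict if behaviour after allocation can be adjudicated as ineligibility. The SAP does not say which applies.

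**2. How far the grounds go beyond entry criteria.** Table 2 has 20 rows, of which 16 repeat rows of Table 1, including the willingness and anticipated-problems rows. The other four are fragility fracture, stress fracture, age under 18 and the catch-all. The first two spell out Table 1's row on lacking an eligible fracture, and age is an objective entry fact. Only the catch-all has no anchor in an entry criterion.

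**3. Whether a planned analysis restores these participants.** In section 3.3, item 1 changes the pain threshold, items 2 and 3 concern the primary site and adherence there, and item 4 is an available-case analysis, which addresses missing outcomes. All of them fall under the section 2.1 exclusion.

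**4. Illustration of size.** The SAP gives no exclusion count, event rate or sample size, so there is no figure to reproduce. All inputs below are assumptions.
- The true effect is null, with overall risk P in both arms.
- A share f of the CBT arm is removed, and nobody from usual care.
- Those removed have k times the risk of those remaining.

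Let r be the risk in those remaining. Then P = (1 − f)·r + f·k·r, so r = P / [(1 − f) + f·k]. The apparent risk ratio is r / P = 1 / [(1 − f) + f·k], which does not depend on P.

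Worked values at k = 1.5:
- f = 5%: 1 / (0.95 + 0.075) = 1 / 1.025 = 0.976
- f = 10%: 1 / (0.90 + 0.15) = 1 / 1.05 = 0.952

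| k | f = 2% | f = 5% | f = 10% | f = 20% |
|---|---|---|---|---|
| 0.75 | 1.005 | 1.013 | 1.026 | 1.053 |
| 1.25 | 0.995 | 0.988 | 0.976 | 0.952 |
| 1.5 | 0.990 | 0.976 | 0.952 | 0.909 |
| 2 | 0.980 | 0.952 | 0.909 | 0.833 |

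**5. Less extreme removal.** If shares fC and fU are removed from the CBT and usual-care arms at the same k, the ratio is [(1 − fU) + fU·k] / [(1 − fC) + fC·k]. Equal shares give 1.00. With fC = 10%, fU = 5% and k = 1.5, it is 1.025 / 1.05 = 0.976. Only the imbalance matters.

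These are crude risk ratios. They ignore covariates, repeated visits and imputation.

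**The case against.** The strongest reply is that the SAP, read as a whole, adjudicates entry eligibility and treats adherence separately. Several places support this.
- Section 2.3 reports participants randomised to CBT by modules completed, starting at zero.
- Tables 5 and 6 have a column for none completed, under all participants randomised to CBT.
- A Figure 1 footnote says follow-up did not depend on how many sessions were done.
- Most Table 2 rows reproduce Table 1, and the footnote describes the table as showing all response options, so it may be no more than a form's pick-list.
- The catch-all row needs Methods Centre approval.
- Adjudication procedure often sits in a protocol or charter, which is not at hand.

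Much of this stands. A reader might infer that CBT non-starters are dropped as ineligible and that intention-to-treat is therefore broken. The documents do not support that, because zero-module participants are plainly expected among those analysed. A reader might also infer that the bias would favour CBT. That is not supported either: the direction depends on the risk of those removed, which the SAP does not give. Nor would one-sided removal be invisible, since Table 2 reports reasons by arm.

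What the reply does not supply is the missing limit. Keeping some non-starters does not say which of them could be coded as unwilling. Blinding the committee does not equalise evidence that arises in one arm. The cited paper is not in the documents and cannot stand in for a rule that the SAP leaves unwritten.

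**Conclusion.** The concern holds as an open possibility in the definition of the analysis set. Section 2.1 permits removal on grounds that are subjective or open-ended, does not restrict the evidence to pre-randomisation records, and is not reconciled with section 3.1. It does not establish that the primary risk ratio will be biased.

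The illustration supports a measured view of size. Under a null effect with CBT-arm-only removal and k between 1.25 and 2, removing 2% moves the risk ratio by 2% or less. Removing 10% moves it to between 0.98 and 0.91. At k = 0.75 the shift is upwards, to 1.03 at 10%. The share removed, its split between arms and the risk of those removed are all assumed. Unequal counts would show in Table 2, but no planned effect estimate would show what they did to the result. This should be fixed, and the change is small.

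**What to change.** 1. In section 2.1, limit exclusion from analysis to ineligibility documented in pre-randomisation records and judged blind to arm and outcome.
2. State there, in line with section 3.1, that anyone flagged for CBT unwillingness, anticipated problems or the catch-all reason on information arising after randomisation stays in the intention-to-treat set.
3. Add to section 3.3 and Table 11 one sensitivity analysis of the primary outcome in all randomised, consented participants, using the primary model.

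The cost is a few sentences of SAP text and one extra model run. The downside is slight dilution from a few ineligible participants who stay in.

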2.3 CBT Compliance

We will report the number of participants randomized to the CBT intervention who completed the CBT modules according to the number of modules completed (0 to 7 modules). We will also look at levels of compliance by key baseline factors including the subgroup analysis factors, participant age (<60 versus ≥ 60), and injury severity (defined as an Injury Severity Score [ISS] greater than or equal to 9). The data will be presented as frequencies and percentages (**Tables 5 and 6**).

2.4 Outcome Completion Rates

We will report on the outcome completion rates at each follow-up visit. The data will be presented as frequencies and percentages (**Table 7**).

3.0 ANALYSIS

3.1 Analysis Methods

The primary and secondary analyses will be conducted following intention-to-treat (ITT) principles, ensuring that participants are analyzed in their originally assigned treatment groups, regardless of adherence or protocol deviations. The date on which the participant's fracture(s) occurred will be used as the starting point for all time-to-event analyses.

We will use multiple imputations to account for missing data in the analyses and minimize potential bias under the assumption that the data are missing at random (MAR). This approach will allow for the uncertainty associated with missing values to be properly accounted for, improving the robustness of statistical inferences.⁴ Additionally, as we anticipate high rates of early withdrawal, we will account for this in the analyses, if needed.

If any of the analysis models fail to converge, we will remove adjustment covariates one by one until convergence is achieved. The same set of covariates will be used consistently across all models in the primary and secondary analyses.

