3.1.2 Secondary Analyses

- 1) *Health-Related Quality of Life (HRQoL)*: We will use linear repeated measures mixed modeling to explore the association between: 1) CBT treatment status and Short Form-36 (SF-36) Physical Component Summary (PCS) scores over 12 months, and 2) CBT treatment status and SF-36 Mental Component Summary (MCS) scores over 12 months. The SF-36 is an established, reliable and validated health status measure.⁵⁻⁷ It measures HRQoL through an 8-domain profile of functional health and well-being, physical and mental health summary measures (PCS and MCS). The SF-36 PCS and MCS are scored on a scale from 0 to 100, with 100 representing the highest level of functioning possible. SF-36 PCS and MCS scores will be included as the dependent variable in each corresponding model. CBT treatment status, stratification variables, and time of assessment (continuous measure in days) will be included in the models as fixed effects, with patients entered as a random intercept. The models will also be adjusted for baseline SF-36 PCS and MCS scores, accordingly, as well as including a time-by-treatment interaction term. Results will be reported using marginal standardization as adjusted mean differences (aMDs) with 95% CIs and p-values (**Table 8**).
- 2) *Return to Function*: We will use Cox proportional hazards regression modeling to explore the association between: 1) CBT treatment status and returning to $\geq 80\%$ of pre-injury functioning, 2) CBT treatment status and returning to full function with respect to work, 3) CBT treatment status and returning to full function with respect to leisure activities, and 4) CBT treatment status and returning to full function with respect to responsibilities around the home. These return to function components are measured using the Return to Function questionnaire, which has been used in a previous fracture trial⁸ documents when participants return to work, household activities, and leisure activities without limitations, as well as when they achieve 80% of their pre-injury function. Participants will be censored at their last documented follow-up visit. The analyses will adjust for stratification variables and the results will be reported as hazard ratios (HRs) with 95% CIs and p-values (**Table 9**).

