Outcome	CBT n (%) (n= XX)	Usual Care n (%) (n= XX)	Estimate** (95% CI)	p-value
Primary Outcome				
Moderate to Severe ($\geq 4/10$) PPSP, adjusted percent (95% CI)				
Secondary Outcomes				
SF-36 PCS, mean (95% CI)				
SF-36 MCS, mean (95% CI)				
BPI-SF Average Pain Severity Score, mean (95% CI)				
BPI-SF Pain Interference Score, mean (95% CI)				
Taking an opioid class medication (6 months)				
Taking an opioid class medication (12 months)				

**Estimates are presented as an adjusted risk ratio for the primary outcome, as an odds ratio for the opioid use outcome, and as adjusted mean differences for the remainder of the secondary outcomes.

Table 9: Impact of CBT versus Usual Care on Return to Pre-Injury Function, Work, and Activities

Function Category	Hazard Ratio (95% CI)	p-value
≥80% of Pre-injury Functioning CBT vs. No CBT		
Work* CBT vs. No CBT		
Leisure Activities CBT vs. No CBT		
Responsibilities around the Home CBT vs. No CBT		

*Unemployed participants were excluded from analyses

Table 10: Impact of CBT versus Usual Care on Moderate to Severe PPSP in Different Subgroups

Subgroup	CBT Adjusted percent (95% CI) (n= XX)	Usual Care Adjusted percent (95% CI) (n= XX)	Adjusted Risk Ratio (95% CI)	p-value
Sex				
Male				
Female				
Fracture Type				
Any open fracture				
No open fracture				
Background/Employment				
Military, veteran, and first responder				
Not a veteran, first responder or employed by the military				
SPOC Score				
Low (≤ 58)				
Medium ($58 < \text{SPOC score} \leq 85$)				
High (>85)				
Site Location				
Canada				
United States				

Table 11: Sensitivity and Exploratory Analyses

Outcome	CBT Adjusted percent (95% CI) (n= XX)	Usual Care Adjusted percent (95% CI) (n= XX)	Adjusted Risk Ratio (95% CI)	p-value
Exploratory Outcome – Any Severity of PPSP				
PPSP Severity Any severity ($\geq 1/10$)				
Primary Outcome - Participants randomized to the CBT intervention at the primary site				
PPSP Severity Moderate to Severe ($\geq 4/10$)				
Primary Outcome – Adherence to at least three CBT modules at the primary site				
PPSP Severity Moderate to Severe ($\geq 4/10$)				
Primary Outcome – Adherence to at least six CBT modules at the primary site				
PPSP Severity Moderate to Severe ($\geq 4/10$)				

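### The return-to-function Cox models start at fracture with no delayed entry and no rule for milestones reached before randomisation, which pulls their hazard ratios toward 1

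*SAP*

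**What the plan says.** Section 3.1 sets one time origin for every time-to-event analysis: the day the fracture "occurred will be used as the starting point for all time-to-event analyses". Section 3.1.2, item 2, holds the only analyses of this kind. It begins "We will use Cox proportional hazards regression modeling to explore the association between" and lists four milestones: at least 80% of pre-injury function, and full return to work, leisure and home responsibilities. The questionnaire behind them "documents when participants return to work, household activities, and leisure activities without limitations", along with the 80% milestone. The one censoring rule is "Participants will be censored at their last documented follow-up visit".

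Tables 1 and 2 in section 4.0 give as a reason for exclusion: "Patient was not screened/approached within 2-12 weeks following their fracture". They also exclude a patient who is "Currently not experiencing any pain in the fracture region despite being fully weight bearing". Table 9 restricts the work analysis in one way: "Unemployed participants were excluded from analyses". The matching objective in section 1.0 is whether CBT "accelerates return to function over 12 months post-fracture".

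The SAP does not mention delayed entry. It does not require a milestone to fall after randomisation, and has no rule for participants who reached one earlier.

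**The concern.** A participant randomised in week 8 is treated as at risk, and labelled CBT or usual care, for eight weeks in which no allocation existed. If that participant was back at work in week 6, the model records an event in the allocated arm that the allocation cannot have affected. Because allocation is random, such events fall evenly across the arms. They add a stretch with a hazard ratio of exactly 1 to the start of follow-up.

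Unlike the primary, SF-36 and BPI-SF models, the Cox models have no time-by-treatment term. That stretch is therefore averaged into the single hazard ratio reported for each milestone. At stake is secondary objective 3: a real acceleration of recovery could be understated or missed on all four milestones.

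**Working it through.** **Inputs from the SAP.** Origin at fracture (3.1). Approach at 2 to 12 weeks (Tables 1 and 2). Cox model with right censoring only (3.1.2). No exclusion for a milestone already reached (Table 9 excludes only the unemployed, and only for work). The SAP gives no hazard ratio, event count or power for these endpoints, so there is no figure of its own to reproduce.

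**Assumptions.** True hazard ratio 1.30 after randomisation and 1 before it. Randomisation uniform over weeks 2 to 12. Equal allocation. Follow-up to 52 weeks from fracture. Weibull times to milestone: shape 1 is a constant hazard from the day of fracture, and a shape above 1 is a hazard that rises as healing proceeds.

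**Step 1, closed form.** Let f be the share of events before randomisation. The fitted log hazard ratio is roughly an event-weighted average of 0 (weight f) and ln HR (weight 1 − f), so HR as written ≈ HR^(1 − f):

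- f = 0.06: 1.30^0.94 = 1.28
- f = 0.21: 1.30^0.79 = 1.23
- f = 0.38: 1.30^0.62 = 1.18

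**Step 2, simulation.** This compares the analysis as written with delayed entry at randomisation and earlier milestones removed.

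| Median time to milestone, shape | Events before randomisation | HR as written | HR with delayed entry |
|---|---|---|---|
| 10 weeks, 1 | 38% | 1.18 | 1.30 |
| 16 weeks, 1 | 28% | 1.21 | 1.30 |
| 26 weeks, 1 | 21% | 1.23 | 1.30 |
| 26 weeks, 1.5 | 11% | 1.26 | 1.30 |
| 26 weeks, 2 | 6% | 1.28 | 1.30 |
| 26 weeks, 3 | 2% | 1.29 | 1.30 |

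The closed form and the simulation agree.

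**Step 3, does removing events cost precision?** With D events in all, the standard error of the log hazard ratio is about 2/√D. As written, z ≈ (1 − f) × ln HR × √D / 2. After the correction, z ≈ ln HR × √((1 − f)D) / 2. The ratio of corrected to as-written is 1/√(1 − f), which is above 1 whenever f > 0. It is 1.03 at f = 0.06, 1.13 at f = 0.21 and 1.27 at f = 0.38. The simulated z values agree: 4.04 against 4.54 at the 26-week median with shape 1, a ratio of 1.12.

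**Step 4, power.** At a hazard ratio of 1.30, 457 events give 80% power if no event precedes randomisation. Power is Φ(z − 1.96). For 457 recorded events and f = 0.20:

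- as written: z = 0.80 × 0.2624 × √457 / 2 = 2.24, power 61%
- corrected, with 0.80 × 457 ≈ 366 events: z = 0.2624 × √366 / 2 = 2.51, power 71%

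At f = 0.10 the figures are 71% and 76%.

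**Step 5, null case.** With a true hazard ratio of 1 and about 29% of events before randomisation, the analysis as written gave a hazard ratio of 1.00 and rejected in 5% of replicates.

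**Step 6, which element does the harm?** With the clock left at fracture and earlier milestones simply removed, the hazard ratio was 1.295 to 1.302 across the settings run with shapes 1 to 2. Removing those events is the main step, and delayed entry completes it.

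**The case against.** The strongest reply is that a fracture clock is the right one, because the objective is framed as time after fracture. That stands. A reader might infer that the choice of origin is itself the error, but the SAP does not support this. The origin fits the objective, and the gap lies in what is missing beside it. Moving time zero to randomisation is not automatically better either. With a steeply rising hazard (shape 3, median 16 weeks), a randomisation clock without a term for time since fracture gave 1.266, against 1.274 as written and 1.30 with delayed entry.

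A second reply is that few patients will be back to full function so early, and that the exclusion of pain-free, fully weight-bearing patients removes some of those who are. This stands as a limit on size: a rising hazard is plausible, and the simulations do not model that exclusion. It does not close the gap. A patient still in pain but already back at work or home duties, or at 80% of function, remains eligible.

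A third reply is that the protocol may cover the matter. Section 3.1 refers all time-to-event analyses to the fracture date without qualification, and an analyst following the SAP would count the early events.

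A reader might also infer that the flaw could produce a false benefit or touch the primary result. Neither follows: type I error is unaffected, and the primary analysis is not a time-to-event model.

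**Conclusion.** The concern holds as a fixable gap in the secondary analyses. As written, milestones reached before randomisation count as outcomes in all four Cox models, so the hazard ratios are attenuated and power is lost.

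The direction follows from the SAP alone. The size does not, because the share of early milestones is not given and may differ between the four. Under the stated assumptions and a true hazard ratio of 1.30, the as-written value runs from about 1.29 (2% early) to 1.18 (38% early). The upper end requires a constant hazard from the day of fracture and a median of only 10 weeks. A claim that the dilution is certainly large would go beyond the document. The SAP also gives the approach window rather than the randomisation date, so the uniform 2 to 12 weeks is an approximation. Nothing can be gained by leaving the rule as it is: the corrected test was stronger in every setting with early events.

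**What to change.** Keep days since fracture as the time scale and add to section 3.1 or 3.1.2 wording such as: *Each participant enters the risk set on the day of randomisation. For each milestone, participants who had already reached it by that day are excluded from the analysis of that milestone, and their number is reported by arm.* In R this is `Surv(day of randomisation, day of event or censoring, status)`, with days counted from fracture. Add the excluded counts to Table 9. If randomisation is used as time zero instead, apply the same exclusion and adjust for time from fracture to randomisation.

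The coding cost is small, but there are two real costs. First, each milestone loses participants and events, from a few percent to over a third depending on how early it is reached. Second, milestone dates must be precise enough to place before or after randomisation. Table 7 lists the Return to Function form only at 3, 6, 9 and 12 months, and Table 3 shows no milestone status at baseline. The SAP should therefore say which recorded date is used and how an unclear one is handled. The rule should be fixed before results by arm are seen, because a later change would look data-driven.
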